### 5.3.2.2 Vital signs

Vital signs include body temperature, blood pressure and pulse measurements. Blood pressure (systolic and diastolic) and pulse should be measured.

For the assessment schedule refer to Table 5-1.

### 5.3.2.3 Height and weight

Height in centimeters (cm) and body weight (to the nearest 0.1 kilogram [kg] in indoor clothing, but without shoes) will be measured. Height will be measured at screening only. For the assessment schedule for weight refer to Table 5-1.

### 5.3.2.4 Performance status

WHO performance status will be assessed as per the assessment schedule (refer to Table 5-1). Assessment of WHO performance status (Table 5-2) will be performed within the time windows described above of the scheduled assessment, even if ceritinib medication is being held. More frequent examinations may be performed at the investigator's discretion, if medically indicated.

**Table 5-2 WHO Performance status scale**

Score	Performance Status
0	Fully active, able to carry on all pre-disease performance without restriction
1	Restricted in physically strenuous activity but ambulatory and able to carry out work of a light or sedentary nature, e.g. light housework, office work
2	Ambulatory and capable of all self-care but unable to carry out any work activities. Up and about more than 50% of waking hours
3	Capable of only limited self-care, confined to bed or chair more than 50% of waking hours
4	Completely disabled. Cannot carry on any self-care. Totally confined to bed or chair
5	Dead

### 5.3.2.5 Laboratory evaluations

Local site laboratories will be used for the analysis of scheduled hematology, biochemistry, urine, and other blood specimens collected as part of safety monitoring. All unscheduled blood testing will be performed locally, with exceptions for emergency conditions. The time windows granted for laboratory evaluations are identical to the corresponding visit time windows for each visit (refer to Section 5.1).

Laboratory abnormalities that are considered clinically significant, induce clinical signs or

symptoms, require concomitant therapy or require changes in ceritinib treatment constitute an adverse event (AE) and must be reported as an AE in the clinical trial record. Laboratory values obtained at the screening visit will be used to assess eligibility to meet inclusion criteria. In addition, eligible patients must have baseline laboratory assessments performed on Cycle 1 Day 1 or within 24 hours prior to dosing.

#### 5.3.2.5.1 Hematology

Hematology assessments of the parameters listed in Table 5-3 will be tested as per the schedule of assessments (Table 5-1).

**Table 5-3 Local Clinical laboratory parameters collection plan**

Test Category	Data Results	Test Name
Hematology		Hgb, platelets, white blood cells (WBC), red blood cells (RBC), differential (basophils, eosinophils, lymphocytes, monocytes, neutrophils (% or absolute))
Chemistry		Albumin, ALT, AST, calcium, creatinine, total bilirubin, direct bilirubin (only if total bilirubin is $\geq$ grade 2), blood urea nitrogen (BUN) or urea, magnesium, potassium, sodium, glucose, phosphate (inorganic phosphorus), alkaline phosphatase, GGT, lipase, amylase
Coagulation		PT/PTT
Creatinine clearance		Creatinine clearance
Urinalysis		Macroscopic panel (dipstick)(color, total bilirubin, blood, glucose, ketones, leukocyte esterase, nitrite, pH, protein, specific gravity, urobilinogen) Microscopic panel (RBC, WBC, casts, crystals, bacteria, epithelial cells)
Pregnancy test		For women of childbearing potential : At screening visit, serum pregnancy test At subsequent cycles, urinary pregnancy test. If local requirements dictate otherwise, local regulations should be followed

#### 5.3.2.5.1 Hematology

Hematology assessments of the parameters listed in Table 5-3 will be tested as per the schedule of assessments (Table 5-1).

#### 5.3.2.5.2 Clinical chemistry and Creatinine clearance

Clinical chemistry and Creatinine clearance assessments of the parameters listed in Table 5-3 will be tested as per the schedule of assessments (Table 5-1).

#### 5.3.2.5.3 Urinalysis

Dipstick measurements will be performed as per Table 5-3 and according to the schedule of assessments (Table 5-1). Any significant findings on dipstick will be followed up with microscopic evaluation as per Table 5-3.

#### 5.3.2.5.4 Pregnancy and assessments of fertility

During screening, a serum pregnancy test will be completed. Starting on day 1 of Cycle 2, and at EOT, urinary pregnancy test (dipstick) will be performed. The time windows granted for pregnancy testing are

identical to the corresponding visit time windows for each visit. If local requirements dictate otherwise, local regulations should be followed.

Women who are determined not to be of child bearing potential before the study will only be tested at screening. When non-child bearing potential status is determined during the study, further pregnancy testing will not be continued. Women are considered post-menopausal if they have had 12 months of natural (spontaneous) amenorrhea with an appropriate clinical profile (e.g. age appropriate, history of vasomotor symptoms), and otherwise not of child bearing potential if they have had surgical bilateral oophorectomy (with or without hysterectomy) or tubal ligation at least six weeks ago. In the case of oophorectomy alone, only when the reproductive status of the woman has been confirmed by follow up hormone level assessment is she considered not of child bearing potential.

The time windows granted for pregnancy testing are identical to the corresponding visit time windows for each visit.

If a positive pregnancy test is performed in between study visits, the patients must immediately notify the investigator.

### 5.3.2.6 Translational analysis

To analyze the immunologic impact of SABR and ceritinib, 16 ml of whole blood (8ml X 2 tubes) will be drawn from patients into BD Vacutainer Whole Blood Tube, ACD A, (Yellow, 8.5 mL), at Cycle 1 Day 1, Cycle 1 Day 15, Cycle 3 and Cycle 6 day 1, and end of treatment.

For circulating ALK biomarker and resistance mechanism analysis, 30 ml of whole blood (10 X 3 tubes) will be drawn into Streck CELL-FREE DNA BCT® at Cycle 1 Day 1, Cycle 1 Day 15, Cycle 3 and Cycle 6 day 1, and end of treatment. Plasma will be processed and frozen for ALK and resistance mechanism analysis. CTCs will be enriched and captured and interrogated for biomarker analysis.

Blood will not be drawn if the investigator is concerned that doing so may harm the patient.

### 5.3.2.7 Cardiac assessments

#### 5.3.2.7.1 Electrocardiogram (ECG)

A standard 12 lead ECG should be used for assessments.

All ECGs will be performed locally and reviewed by investigator prior to ceritinib treatment administration. Please refer to Table 5-4 for cardiac assessment monitoring schedule.

Table 5-4 ECG collection plan

Cycle	Day of cycle	ECG monitoring a
	Screening b	1 single ECG
Cycle 1	1	Pre-dose: 3 sequential ECGs separated by at least 2-4 minutes
Cycle 2	1	Pre-dose: 1 single ECG
Even numbered cycles (4,6,8...)	1	Pre-dose: 1 single ECG
EOT	N/A	1 single ECGs recorded

a Refer to Table Criteria for interruption and re-initiation of ceritinib treatment for the recommended dose modifications due to QTc interval prolongation  
b The screening ECGs will be reviewed by investigator for eligibility of the patient. (Note: the mean QTc interval at baseline must be  $\leq 450$  msec for the patient to be eligible for participation in the trial)  
Note: Additional monitoring performed at the Investigator's discretion, if medically indicated.

Interpretation of the tracing must be made by a qualified physician and documented. Clinically significant abnormalities present when the patient signs the informed consent should be reported. New or worsened clinically significant findings occurring after informed consent must be recorded.

## 6.0 Measurement of Effect

### 6.1 Antitumor Effect- Solid Tumors

Response and progression will be evaluated in this study using the new international criteria proposed by the Response Evaluation Criteria in Solid Tumors (RECIST) Committee [JNCI 92(3):205-216, 2000]. Changes in only the largest diameter (unidimensional measurement) of the tumor lesions are used in the RECIST v1.1 criteria.

#### 6.1.1 Definitions

Evaluable for toxicity. All subjects will be evaluable for toxicity from the time of their first treatment with study drug.

Evaluable for objective response. Only those subjects who have measurable disease present at baseline, have received at least one cycle of therapy, and have had their disease re-evaluated will be considered evaluable for response. These subjects will have their response classified according to the definitions stated below. (Note: Subjects who exhibit objective disease progression prior to the end of cycle 1 will also be considered evaluable.)

#### 6.1.2 Disease Parameters

Measurable disease. Measurable lesions are defined as those that can be accurately measured in at least one dimension (longest diameter to be recorded) as  $\geq 20$  mm with conventional techniques (CT, MRI, x-ray) or as  $\geq 10$  mm with spiral CT scan. All tumor measurements must be recorded in millimeters (or decimal fractions of centimeters).

Note: Previously irradiated lesions are non-measurable except in cases of documented progression of the lesion since the completion of radiation therapy.

Non-measurable disease. All other lesions (or sites of disease), including small lesions (longest diameter  $< 20$  mm with conventional techniques or  $< 10$  mm using spiral CT scan), are considered non-measurable disease. Bone lesions, leptomeningeal disease, ascites, pleural/pericardial effusions, lymphangitis cutis/pulmonis, inflammatory breast disease, abdominal masses (not followed by CT or MRI), and cystic lesions are all non-measurable.

Target lesions. All measurable lesions up to a maximum of 3 lesions per organ and 6 lesions in total, representative of all involved organs, should be identified as **target lesions** and recorded and measured at baseline. Target

lesions should be selected on the basis of their size (lesions with the longest diameter) and their suitability for accurate repeated measurements (either by imaging techniques or clinically). A sum of the longest diameter (LD) for all target lesions will be calculated and reported as the baseline sum LD. The baseline sum LD will be used as reference by which to characterize the objective tumor response.

Non-target lesions. All other lesions (or sites of disease) including any measurable lesions over and above the 6 target lesions should be identified as **non-target lesions** and should also be recorded at baseline. Measurements of these lesions are not required, but the presence or absence of each should be noted throughout follow-up.

### **6.1.3 Methods for Evaluation of Measurable Disease**

All measurements should be taken and recorded in metric notation using a ruler or calipers. All baseline evaluations should be performed as closely as possible to the beginning of treatment and never more than 30 days before the beginning of the treatment.

The same method of assessment and the same technique should be used to characterize each identified and reported lesion at baseline and during follow-up. Imaging-based evaluation is preferred to evaluation by clinical examination when both methods have been used to assess the antitumor effect of a treatment.

Conventional CT and MRI. These should be performed with cuts of 10 mm or less in slice thickness contiguously. Spiral CT should be performed using a 5 mm contiguous reconstruction algorithm.

CT scans of the neck, chest, abdomen and pelvis will be performed at baseline and every two cycles according to standard of care. Other imaging of these areas such as PET/MRI will be allowed if CT cannot be performed. MRI of the brain will be performed at baseline and as clinically indicated. Wherever it can be safely given, radiographic contrast agents should be given for the imaging studies.

### **6.1.4 Response Criteria**

#### **6.1.4.1 Evaluation of Target Lesions**

Complete Response (CR): Disappearance of all target lesions, determined by two separate observations conducted not less than 4 weeks apart. There can be no appearance of new lesions.

Partial Response (PR): At least a 30% decrease in the sum of the longest diameter (LD) of target lesions, taking as reference the baseline sum LD. There can be no appearance of new lesions.

Progressive Disease (PD): At least a 20% increase in the sum of the LD of target lesions, taking as reference the smallest sum LD recorded since the treatment started, or the appearance of one or more new lesions.

Stable Disease (SD): Neither sufficient shrinkage to qualify for PR nor sufficient increase to qualify for PD, taking as reference the smallest sum LD since the treatment started.

#### 6.1.4.2 Evaluation of Non-Target Lesions

Complete Response (CR): Disappearance of all non-target lesions and normalization of tumor marker level.

Incomplete Response/Stable Disease (SD): Persistence of one or more non-target lesion(s) and/or maintenance of tumor marker level above the normal limits.

Progressive Disease (PD): Appearance of one or more new lesions and/or unequivocal progression of existing non-target lesions

#### 6.1.4.3 Evaluation of Best Overall Response

The best overall response is the best response recorded from the start of the treatment until disease progression/recurrence (taking as reference for progressive disease the smallest measurements recorded since the treatment started). The subject's best response assignment will depend on the achievement of both measurement and confirmation criteria.

Target Lesions	Non-Target Lesions	New Lesions	Overall Response	Best Response for this Category Also Requires:
CR	CR	No	CR	≥4 wks. confirmation
CR	Non-CR/Non-PD	No	PR	≥4 wks. confirmation
PR	Non-PD	No	PR	
SD	Non-PD	No	SD	Documented at least once ≥4 wks. from baseline
PD	Any	Yes or No	PD	no prior SD, PR or CR
Any	PD*	Yes or No	PD	
Any	Any	Yes	PD	

* In exceptional circumstances, unequivocal progression in non-target lesions may be accepted as disease progression.
 
Note: Subjects with a global deterioration of health status requiring discontinuation of treatment without objective evidence of disease progression at that time should be reported as "symptomatic deterioration". Every effort should be made to document the objective progression even after discontinuation of treatment.
				

Note: If subjects respond to treatment and are able to have their disease resected, the patient's response will be assessed prior to the surgery.

### 6.1.5 Duration of Response

Duration of overall response: The duration of overall response is measured from the time measurement criteria are met for CR or PR (whichever is first recorded) until the first date that:

- i. recurrent or progressive disease is objectively documented (taking as reference for progressive disease the smallest measurements recorded since the treatment started) AND is amenable to SABR. This will be defined as time to subsequent SABR.
- ii. recurrent or progressive disease is objectively documented (taking as reference for progressive disease the smallest measurements recorded since the treatment started) and is NOT amenable to SABR. This will be defined as progression on systemic therapy.

The duration of overall CR is measured from the time measurement criteria are first met for CR until the first date that recurrent disease is objectively documented.

### 6.1.6 Progression-Free Survival

Progression Free Survival will be the primary endpoint for this study. If oligoprogression occurs that is amenable to repeat treatment with SABR, the ceritinib will be held and SABR therapy delivered. If the treating oncologist then feels the patient would benefit from continuing the ceritinib that will be permitted. The patient will however be deemed as having progressed even if ceritinib is resumed.

After the initial SABR to persisting lesions if new lesions appear or if existing lesions enlarge but are NOT amenable to SABR (necessitating a change in systemic therapy), the patient will have completed the therapeutic portion of the study.

Time to 2nd SABR is defined as the duration of time from the start of treatment to the time of development of new or enlarging lesions that are amenable to SABR and the progression does not require a discontinuation of ceritinib.

Time to 3rd SABR is defined in patients who have already received two rounds of SABR while on this study as the duration of time from the start of treatment to the time of development of new or enlarging lesions that are amenable to SABR and the progression does not require a discontinuation of ceritinib.

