**Hypothesis:**

The primary objective is to describe the PFS in patients undergoing study therapy. This is defined as evidence of disease progression by RECIST, unacceptable toxicity, withdrawal of consent, or discontinuation of the trial for any other reason.

Additional SABR to enlarging lesions will be permitted while on ceritinib, but no change in systemic therapy will be allowed. Patients who demonstrate oligo progression and have disease amenable to repeat courses of radiation therapy may resume ceritinib at the discretion of the treating oncologist until a change in systemic therapy is indicated.

The secondary objective of the study is to report overall survival and in *ALK*-positive lung adenocarcinoma. We will use Kaplan-Meier methods to estimate the overall survival. The rate of overall response and its 95% confidence interval will be estimated using exact binomial method. Response duration will be summarized for patients who responded. Descriptive summary statistics like median, 25% and 75% percentiles will be used.

The secondary objective is also to describe the time to subsequent SABR in patients undergoing study therapy. Patients will be retreated with SABR if feasible. After the initial SABR to persisting lesions, if new lesions appear or if existing lesions enlarge but are amenable to SABR, patients will remain on study and listed as not having progressed. This time to 2nd and 3rd SABR will be recorded and reported. The secondary endpoint will be recorded as time to 2nd and (if applicable) 3rd SABR therapy.

The safety objective of this study to report the toxicity profile of the combination of ceritinib and SABR therapy. Both are well tolerated and routinely used in non-small cell lung cancer.

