## 8.2 Therapy Stereotactic Ablation Body Radiation (SABR)

### 8.3 SABR DOSE AND TECHNIQUES

SABR will begin 10 weeks after initiation of ceritinib for consolidation of residual disease sites.

Additional SABR treatments will be delivered to new distinct areas of disease that develop after that period at the discretion of the treating medical oncology/radiation oncology teams. PFS will at that point already been established, but patients will be followed for OS.

Stereotactic treatment is the targeting, planning, and directing of treatment fields guided to a target based on known 3-D coordinates related to reliable fiducial markers. This differs from conventional radiation therapy in which treatment is guided by skin or bony landmarks assumed to correlate to the target volume based on the initial simulation. SABR in this study will be delivered with an ablative range of dose per fraction. Treatment will account for inter/intra-fractional errors with careful dosimetry that delivers an ablative dose to the metastatic lesion(s) while respecting normal tissue constraints.

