**Study Design:**

**Purpose:** of this prospective, single-center, two cohort, non-randomized trial is to evaluate the impact of the combination of ceritinib and stereotactic radiation delivered to patients with *ALK*-rearranged adenocarcinoma. The enhanced efficacy of this combination is to be evaluated specifically with regards to prolongation of clinical benefit of ceritinib. We will also evaluate the safety of this combination of targeted therapy and radiation.

For *ALK*-rearranged patients started on ceritinib and treated with SABR to persisting lesions:  
 -PFS compared to published historical results with ceritinib alone PFS=7 month for prior crizotinib treated and 10 month for no previous crizotinib therapy (Shaw et al, NEJM 2014).  
 PFS will be defined as Time to Subsequent Systemic Therapy.

As secondary objectives, we will also report overall survival and time to 2nd and 3rd SABR for each cohort.

	Objective	Endpoint
Primary:	Cohort A: Superiority of ceritinib + SABR median PFS compared to historical control of 10 months (expected to be 20 months)  Cohort B: Superiority of ceritinib + SABR median PFS compared to historical control of 7 months	Cohort A Median PFS defined as time from initiation of ceritinib until disease progression by RECIST 1.1, unacceptable toxicity, withdrawal of consent, or discontinuation of the trial for any other reason including death.  Cohort B: Median PFS defined as time from initiation of ceritinib until disease progression by RECIST 1.1, unacceptable toxicity, withdrawal of consent, or discontinuation of the trial for any other reason including death.
Secondary:	Report Overall survival  Report Time to 2 nd SABR  Report Time to 3 rd SABR  Report proportion of patients CR/PR/stable disease at 6 and 12 months	Overall survival  Time from start of systemic therapy to first day of second course of SABR  Time from start of therapy to first day of third course of SABR  Number of patients with CR/PR/stable disease for 6 and 12 months after initiation
Safety:	Demonstrate safety of ceritinib followed by SABR	Describe toxicity and adverse events (CTCAE v.4) compared to historical controls.

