## 9.3 Data Analyses Plans

We will use Kaplan-Meier methods to estimate the progression-free survival, time to 2nd and 3rd SABR and overall survival.

Duration of response (defined in 6.1.5) duration will be summarized for patients who responded. Descriptive summary statistics like median, 25% and 75% percentiles will be used.

Toxicities are dichotomized as none versus any, or none and mild versus moderate to severe.

The rates of overall response, toxicity and adverse events as well as their 95% confidence intervals will be estimated using exact binomial method.

We will compare the rates of toxicity and adverse events in this study with those of historical controls by the Fisher's exact test.

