### **9.7 Statistical methods and data analysis**

### **9.8 Analysis sets**

#### **9.8.1 Full Analysis Set**

The Full Analysis Set (FAS) comprises all enrolled patients.

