#### **9.10.1 Handling of missing values/censoring/discontinuations**

All attempts will be made to ensure that the database contains full information for the safety set. No imputation will be applied for missing data.

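### Time to 3rd SABR has two conflicting definitions, and the Section 6.1.6 one, analysed by Kaplan-Meier as planned, counts time in which the event cannot occur

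*Combined protocol and SAP*

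**What the plan says.** Time to 3rd SABR is a secondary endpoint in both cohorts (Section 2.0 and the Section 9.1 table). It is defined twice.

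- Section 6.1.6 limits who is counted and sets the origin of the clock: "in patients who have already received two rounds of SABR while on this study as the duration of time from the start". Its stopping point is worded separately, and the interval runs "to the time of development of new or enlarging lesions that are amenable to SABR and the progression does not require a discontinuation of ceritinib". The Time to 2nd SABR definition just above it carries no restriction to patients with earlier courses.
- The endpoint table in Section 9.1 gives "Time from start of therapy to first day of third course of SABR", with no condition on earlier courses.

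Section 9.3 sets the method: "We will use Kaplan-Meier methods to estimate the progression-free survival", and the same sentence extends it to time to 2nd and 3rd SABR and to overall survival. No section states a risk set, delayed entry or competing events for this endpoint. Section 9.8.1 says "The Full Analysis Set (FAS) comprises all enrolled patients" but does not tie that set to it. Section 9.10.1 has censoring in its heading, yet on missing data says only "No imputation will be applied for missing data".

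The endpoint's role is descriptive. Section 2.0 says: "The secondary objective is also to describe the time to subsequent SABR in patients undergoing study therapy".

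**The concern.** An analyst who follows Section 6.1.6 selects patients on something that happens after time zero (a second course) and still starts the clock at the first ceritinib dose. Nobody in that set can have the event before their own second course, yet Kaplan-Meier without delayed entry counts them as at risk throughout.

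An analyst who follows Section 9.1 uses other patients and another end date. The two could report different results for the same named endpoint, and the plan does not say which governs.

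A second problem lies beside the first. Section 1.3.3 ends participation when new sites cannot feasibly be irradiated or ceritinib is no longer the systemic agent. Those events, and death, rule out a third course. If they are censored in the usual way, the curve estimates the chance of a third course as though they could not happen.

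**Working it through.** The plan states no figure for this endpoint, so there is none to reproduce. The sample sizes of 18 and 15 rest on PFS alone.

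**The two definitions side by side**

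| | Section 6.1.6 | Section 9.1 table |
|---|---|---|
| Population | patients with two courses already | no restriction |
| Clock starts | start of treatment | start of therapy |
| Event | amenable lesions develop | first day of third course |

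Only 6.1.6 combines selection on a later event with a clock from treatment start. If everyone is followed from the start under 9.1, the built-in event-free time does not arise.

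**Illustration of size.** Inputs from the documents: historical median PFS of 10 months (Cohort A) and 7 months (Cohort B), accrual 36 months and follow-up 12 months (Section 9.2). Assumptions that are mine: the gap to first progression and the gap from second course to next progression are each exponential with the cohort's median m; each progression is SABR-amenable with probability q, taken as 0.3, 0.5 and 0.7; a non-amenable progression ends eligibility; administrative censoring is uniform over 12 to 48 months. Results are from 400,000 simulated patients, with closed forms where they exist:

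- Kaplan-Meier median from the second course, censoring non-amenable progression: m/q. For m = 10: 10/0.3 = 33.3, 10/0.5 = 20, 10/0.7 = 14.3 months.
- True 24-month incidence in all treated patients: q² × [1 − e^(−x)(1 + x)], with x = 24 × ln 2/10 = 1.664. The bracket is 0.495, giving 4.5%, 12.4% and 24.3%.

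| q (m = 10) | Person-time before 2nd course | KM median, 6.1.6 | KM median from 2nd course | 24-month 1 − KM, 6.1.6 | 24-month incidence, all treated |
|---|---|---|---|---|---|
| 0.3 | 50% | 47 | 33 | 22% | 4.5% |
| 0.5 | 50% | 34 | 20 | 34% | 12% |
| 0.7 | 50% | 27 | 14 | 44% | 24% |

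For m = 7 and q = 0.5 the medians are 25 against 14 months, and the 24-month figures 48% against 17%.

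**Adding the lead-in.** Section 8.3 says "SABR will begin 10 weeks after initiation of ceritinib for consolidation of residual disease sites". Starting the first gap after those 10 weeks raises the event-free share to 54–56%. At the target medians with q = 0.7, the Kaplan-Meier median is 46.6 against 28.7 months (Cohort A, 20 months) and 36.5 against 20.1 (Cohort B, 14 months).

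**What drives the percentage gap (m = 10, q = 0.5).** All treated: 12.4%. Restricting to patients whose first progression is amenable: 0.495 × 0.5 = 25%. Also requiring the second course before data cut-off: 28%. Censoring non-amenable progression in Kaplan-Meier: 34%. Each step is selection or censoring. The early clock works the other way: counted from the second course, 1 − KM at 24 months is 1 − 2^(−24/20) = 56%, against 34% from treatment start. Unrestricted Kaplan-Meier in all treated patients still gives 20% against the true 12.4%, so competing events matter under either definition.

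**Expected counts (q = 0.5, no lead-in, historical medians).** Cohort A: 7.6 of 18 reach a second course and 2.6 a third event. Cohort B: 6.9 of 15 and 2.8. Over q = 0.3 to 0.7, third events number 0.9 to 5.1 (A) and 1.0 to 5.4 (B). At the target medians with the lead-in they number 0.4 to 2.2 and 0.5 to 2.8.

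**The case against.** The strongest reply is that Section 9.1 already holds a sound population, and that 6.1.6 may only be saying who can have a third course. Section 2.0 likewise speaks of patients on study therapy and records a third course where it applies. That reading is possible, and it is why the point is a conflict between definitions and not a settled error in both places. It does not remove the problem: the restriction is written into the 6.1.6 definition, is absent from the Time to 2nd SABR definition beside it, and nothing says that 9.1 prevails.

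Two stronger readings are tempting, and the documents do not support them.

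- That the endpoint describes no real population. Patients with two courses are a real, small, selected group. They simply cannot be identified when the clock starts.
- That the gap of 34% against 12% measures immortal time. It does not. Event-free time delays events and lowers the cumulative probability; the gap comes from selection and from censoring competing events.

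The comparator medians from the second course are also not clean, because they too censor competing events. With q = 0.5 the true cumulative incidence from the second course cannot exceed 50%, so in follow-up of this length it reaches no median.

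The reply that impact is small stands: no test, comparator or sample size is attached, and the plan never claims that this endpoint measures the benefit of the second course.

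**Conclusion.** The point holds as a conflict of definitions, one of which is wrong as written for the planned method. Under Section 6.1.6 the time to each patient's own second course is event-free by construction, so the median answers neither of the two questions a reader would bring to it. Kaplan-Meier as usually applied also overstates the probability of a third course, whichever definition is used; the plan does not state how competing events are handled, so this assumes ordinary censoring.

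The event-free share of about half and the medians are illustrative. They depend on exponential gaps with equal medians and on an amenable rate that the documents do not give. The direction of the median shift does not depend on that rate, since the same patients are timed from an earlier origin.

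The effect stops at one descriptive secondary endpoint resting on perhaps two or three events per cohort at a rate of 0.5. It should be corrected, but it does not touch the primary analysis.

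**What to change.** Use one definition, with one end event, in Sections 6.1.6 and 9.1. Choose either the date amenable lesions are documented or the first day of the course, and apply the same choice to Time to 2nd SABR.

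- Preferred: cumulative incidence of a third course from first ceritinib dose in all treated patients (the Safety Set of Section 9.8.2), with death, non-amenable progression and ceritinib discontinuation as competing events.
- Alternatively or in addition: in patients with two courses, time from the second to the third course, with the same competing events.

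In Section 9.3, replace Kaplan-Meier for this endpoint with a cumulative incidence estimator, and state the censoring rule in Section 9.10.1. Report the number of patients reaching each course; with so few events, these counts will tell more than a median.

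The cost is protocol and analysis-plan wording. No new data are needed.
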